15.8 Sample Size Justification

Anticipated annual accrual is approximately 40-45 subjects.

Our general philosophy regarding Phase II trials of new drug combinations is to facilitate the prompt discovery of inactive agents, yet allow for a reasonable estimate of the response rates for those regimens demonstrating some degree of activity. However, excessive accrual to inactive study regimens to document precise response rates is to be avoided. The purpose of this study is to evaluate the activity and potential toxicity of the combination therapy of Imiquimod + HPV vaccine in subjects with untreated high-grade CIN 2,3 cervical dysplasia. This study will implement a 3 arm randomized trial design that will allow us to estimate the treatment effect of Imiquimod + HPV vaccine compared to observation as well as Imiquimod alone compared to observation.

Based on published literature for the primary outcome,³⁸ we assume a 28% spontaneous histological regression rate in CIN 2-3 lesions with observation alone (control group). From Grimm et al.'s efficacy

HIC#: 1603017415 Protocol version 11.0

trial of imiquimod for treatment of CIN 2-3, we would like to have sufficient power to detect a 35% absolute increase in rate of histologic regression in the imiquimod only arm compared to control. Based on this data, we consider a conservative effect size estimate also of an absolute 35% higher rate of histologic regression in the imiquimod + HPV vaccine intervention arm compared with the control arm. We therefore aim to recruit a total sample size of 114 subjects (38 in each arm). Calculations based on Fisher's Exact Test indicate we will have $\geq 90\%$ power to detect a treatment effect of $\geq 29\%$ in both treatment arms independently compared to the observation arm ($\alpha = 0.025$ for each comparison to control). In addition, with n = 38 subjects per arm, we would have 80% power to detect a treatment effect size of $\geq 25\%$ in one treatment arm compared to placebo (while maintaining 90% power to detect the treatment effect size of $\geq 25\%$ in the other arm). Assuming a subject dropout rate of 20%, a total sample size of 138 (n = 46 per arm) subjects is calculated which will be recruited over 5 years.

Some operating characteristics of the study design are as follows:

Exact Operating Characteristics for the Treatment Effect Size Δ given control group rate=0.28, n=38 subjects per arm, one-sided α

Exact binomial probabilities for α given minimum required power = (1- β)								
Δ =	0.00	0.10	0.20	0.30	0.32	0.35	0.37	0.40
(1-β) ≥ 0.80	0.8080	0.8008	0.8101	0.8126	0.8011	0.8168	0.8119	0.8113
α =	0.5321	0.7745	0.1537	0.0366	0.0220	0.0118	0.0058	0.0027
(1-β) ≥ 0.90	0.9033	0.9009	0.9049	0.9060	0.9068	0.9062	0.9012	0.9009
α =	0.4835	0.6574	0.2876	0.0863	0.0616	0.0363	0.0203	0.0103
Exact binomi	Exact binomial probabilities for power = $(1-\beta)$ given maximum required α							
Δ =	0.00	0.10	0.20	0.30	0.32	0.35	0.37	0.40
α ≤ 0.025	0.0147	0.0147	0.0143	0.0140	0.0140	0.0143	0.0146	0.0149
1-β =	0.0147	0.1050	0.3472	0.6860	0.7472	0.8269	0.8706	0.9215
α ≤ 0.05	0.0305	0.0327	0.0272	0.0304	0.0317	0.0330	0.0331	0.0323
1-β =	0.0305	0.1795	0.4847	0.7870	0.8328	0.8898	0.9197	0.9535

Software: G*Power version 3.1.9.2, ©1992-2014, Franz Faul, Universität Kiel, Germany

At 7-8 months from time of initial CIN 2,3 diagnosis, persistent or progressing dysplasia will be surgically excised per current standard of care. Risk of progression of high-grade cervical dysplasia during the study period in the observation group is very low and observation periods of 6-9 months for CIN 2,3 are commonly described in the literature.^{24,39} In this regard, studies estimating the risk of clinical progression from CIN2/3 lesions to cervical cancer found that the median time was 23.5 years with only 1.6% of these lesions becoming invasive within 10 years⁴⁰. In addition, any clinical concern for disease progression based on history, physical exam or colposcopy at an interval follow up visit will trigger cervical biopsies to objectively evaluate histopathology and, should disease progression be noted, the subject will be removed from study and offered surgical excision. We will also employ early stopping rules as follows:

Evaluability for Efficacy and Toxicity:

Only those subjects who are deemed "ineligible" will be eliminated from the analysis. All subjects who receive any therapy will be evaluated for both treatment efficacy and toxicity. While on occasion, circumstances may prevent the determination of treatment efficacy, such subjects will be included in the

HIC#: 1603017415 Protocol version 11.0

analysis and labeled as "unknown". This category will be listed and be reflected in the calculation of the response rate.

References

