15.1 General Statistical Considerations

- Type I error for hypothesis testing will be $\alpha = 0.05$, and 95% confidence intervals will be used for parameter estimation, unless otherwise specified. Type II error will be based on $\beta = 0.10$, unless otherwise specified. Only the primary analysis will use an adjustment for multiple comparisons.
- Summary statistics for continuous variables will include (but may not be limited to) the number of observations, mean, standard deviation, minimum, median and maximum. For categorical variables, summary statistics will include (but may not be limited to) counts, percentages, and cross-tabulation tables.
- Standard diagnostics will be performed to assess whether the assumptions for specific parametric statistical methods are adequately supported by the data. Should parametric methods be inappropriate, the analogous non-parametric methods will be used and only these results will be reported.
- Imputation of missing values will not be applied.
- No interim analyses for efficacy or futility are planned, although the trial may be stopped early based on observations from continual safety monitoring.
- Data analysis will be conducted using SAS® v9.4 (or later).

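### Section 15.8 claims at least 90% power at 29 points and 80% and 90% at 25 points; the planned Fisher test gives 65.3% and 51.6%, and the plan's own table contradicts the claims

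*Combined protocol and SAP*

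**What the plan says.** Section 15.8 takes a control regression rate of 28% and a planning effect of 35 points: "we would like to have sufficient power to detect a 35% absolute increase in rate of histologic regression in the imiquimod only arm". It uses the same 35 points for imiquimod plus vaccine. It sets 38 evaluable subjects per arm and then makes two power statements, both for Fisher's exact test at 0.025 per comparison.

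- First statement: "\geq 90\%$ power to detect a treatment effect of $\geq 29\%$ in both treatment arms independently compared to the observation arm".
- Second statement: "we would have 80% power to detect a treatment effect size of $\geq 25\%$ in one treatment arm compared to placebo", followed by "while maintaining 90% power to detect the treatment effect size of $\geq 25\%$ in the other arm".

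Below these sentences is a table of exact operating characteristics for the same setting: control rate 0.28, 38 per arm, one-sided alpha. In the row for alpha at most 0.025, power at effects of 0.30, 0.32, 0.35, 0.37 and 0.40 is "0.6860 0.7472 0.8269 0.8706 0.9215".

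Section 15.5 confirms the test as one-sided Fisher at 0.025 for each comparison with control. Section 15.1 sets the general standard: "Type II error will be based on $\beta = 0.10$, unless otherwise specified".

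**The concern.** The prose and the table describe the same test, sample size, alpha and control rate, so they should agree. Power rises with the effect. If it is 68.6% at 30 points, it cannot be 90% at 29 points, nor 80% or 90% at 25. The second statement also conflicts with itself, because it gives two different powers for the same effect, sample size, alpha and control rate.

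These sentences are the only statement of power in words for the two co-primary comparisons. A reader who relies on them would think that a 25- to 29-point benefit is unlikely to be missed, and could take a non-significant result as good evidence against a moderate benefit.

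**Working it through.** **Inputs, all from the plan.** Control rate p0 = 0.28; n = 38 evaluable per arm; one-sided Fisher's exact test at 0.025 per comparison (sections 15.5 and 15.8). Effects: 25 points (28% v 53%), 29 points (28% v 57%) and 35 points (28% v 63%).

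**Formula.** Let X1 ~ Binomial(38, p0 + d) and X0 ~ Binomial(38, 0.28), independent. For each of the 39 × 39 outcomes, the one-sided Fisher p-value is the hypergeometric tail P(X1 ≥ x1 | X1 + X0 = x1 + x0). Power is the sum of P(X1 = x1) × P(X0 = x0) over outcomes with a p-value of at most 0.025.

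**Step 1: reproduce the plan's table.** The enumeration returns the power row for alpha at most 0.025 to four decimals.

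| Effect d | 0.00 | 0.10 | 0.20 | 0.30 | 0.32 | 0.35 | 0.37 | 0.40 |
|---|---|---|---|---|---|---|---|---|
| Plan's table | 0.0147 | 0.1050 | 0.3472 | 0.6860 | 0.7472 | 0.8269 | 0.8706 | 0.9215 |
| Recalculated | 0.0147 | 0.1050 | 0.3472 | 0.6860 | 0.7472 | 0.8269 | 0.8706 | 0.9215 |

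The power row for alpha at most 0.05 also reproduces, so the method is the one behind the plan's table.

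**Step 2: apply it to the effects named in the sentences.**

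| Effect | Power stated | Exact power | Chance of missing the effect |
|---|---|---|---|
| 29 points | at least 90% | 65.3% (0.6535) | 1 − 0.6535 = 34.7% |
| 25 points | 80% in one arm, 90% in the other | 51.6% (0.5161) | 1 − 0.5161 = 48.4% |
| 35 points | none in the text; 0.8269 in the table | 82.7% | 17.3% |

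Solving for the effect, power reaches 80% at 33.9 points and 90% at 38.6 points.

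**Step 3: check against the table alone.** It has no 25- or 29-point column, but power increases with the effect. Power at 29 points must therefore be below 0.6860, and power at 25 points must lie between 0.3472 and 0.6860.

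The upper half of the table agrees. Its alpha rows for effects of 0.30 to 0.40 are "0.0366 0.0220 0.0118 0.0058 0.0027" (power at least 0.80) and "0.0863 0.0616 0.0363 0.0203 0.0103" (power at least 0.90). At 30 points, 80% power therefore comes with alpha 0.0366 and 90% with 0.0863, both above 0.025.

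**Step 4: try other readings.**

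| Reading | 25 points | 29 points |
|---|---|---|
| Unsplit one-sided 0.05, 38 per arm | 64.8% | 76.2% |
| All 46 recruited per arm evaluable, 0.025 | 60.6% | 74.3% |
| 46 per arm and unsplit 0.05 | 74.7% | 85.7% |
| Pooled normal approximation, 0.025, 38 per arm | 60.6% | 73.4% |
| At least one of the two tests significant, shared control | 68.3% | 80.9% |
| Both tests significant, shared control | 35.0% | 49.8% |

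None reaches the stated figures. With 38 per arm, 90% power at 29 points needs a Fisher cut-off of about 0.125, five times the planned 0.025. At 0.025, the stated powers would need about 67 per arm (90% at 29 points), 68 per arm (80% at 25 points) and 86 per arm (90% at 25 points).

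**The case against.** The arithmetic is not in dispute; the case on the other side concerns weight and supporting detail.

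- **The right figures are already printed.** The table, including 0.8269 at 35 points, is directly below the sentences, and section 15.1 allows a departure from 90% power where one is specified. The planning effect keeps more than 80% power, and no dose, patient number or analysis decision depends on the 25- and 29-point claims. This limits the damage. It does not make the sentences true, and nothing in the section states that 83% is a chosen departure from the 90% default.
- **The effects may be misprints.** If 29 were meant as 39, power would be 90.6%; if 25 were meant as 35, it would be 82.7%. This is plausible but cannot be shown, and it does not save the claim of 90% for the other arm. The text would need correcting either way.
- **The upper half of the table needs care.** Its alphas are attained sizes at the treated rate, not Fisher cut-offs. It lists 90% power at 37 points with 0.0203 and 80% at 32 points with 0.0220, although power at the planned cut-off is only 0.8706 and 0.7472 there. The point stands. At 30 points the inference is safe because attained size cannot exceed the cut-off (the cut-offs are about 0.053 and 0.123), and the lower half is sufficient without it.
- **One calculation does give a high figure.** A one-sample binomial test against a fixed 28% has 95.4% power at 29 points. But the sentence names Fisher's test and a comparison with the observation arm, and the one-sample test gives 88.2% at 25 points, which does not fit the 80% and 90% pair.

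**Conclusion.** Both power statements in section 15.8 are wrong as written. The shortfall at 29 points is about 25 percentage points (90 − 65.3 = 24.7). At 25 points it is about 28 for one arm (80 − 51.6 = 28.4) and 38 for the other (90 − 51.6 = 38.4). The result rests only on the plan's own assumptions: control rate 28%, 38 evaluable per arm, and a one-sided Fisher test at 0.025 per comparison.

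The fault lies in the stated power, not in the test, the alpha or the conduct of the trial. At 35 points each comparison has 82.7% power, enough by an 80% standard but below the section 15.1 default. Because the sentences justify the sample size for both co-primary tests and contradict the table beneath them, they must be corrected.

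**What to change.** Delete the 29-point and 25-point sentences in section 15.8 and put in their place:

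> With 38 evaluable subjects per arm, a control rate of 28% and a one-sided Fisher's exact test at 0.025 per comparison, power per comparison is about 83% for a 35-point increase, 80% for an increase of about 34 points and 90% for an increase of about 39 points.

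Add one statement in section 15.8 that power at the 35-point planning effect is 83% rather than the default 90%. Section 15.1 already allows this and needs no edit.

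The cost is two sentences and a less favourable stated power. No patients are added, and the test, alpha and sample size stay as they are.

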samples (may be drawn after randomization but must be drawn prior to treatment), endocervical specimen to be sent to Yale Pathology for high-risk HPV DNA testing (if high-risk HPV DNA results are already available, this testing may not have to be repeated) and a second endocervical cytobrush specimen for translational research purposes. Blood samples will be collected in sodium heparin tubes with about 28 cc collected each time as follows: 7 cc in each of 3 green top tubes and 7 cc in 1 EDTA/purple top tube (see follow up visits below). Endocervical specimen for high-risk HPV DNA test to be performed by Yale Pathology will be submitted in usual fashion as a SurePath specimen. Endocervical cytobrush sample for study purposes will be collected into a 50ml conical tubes containing PBS using sterile techniques and will be stored on ice until picked up by a laboratory personnel. Once all eligibility has been met the subject will be randomized to one of three arms.

Additional components of visit outline by study group:

- (1) Control group: Observation at specified study timepoints.
- (2) Imiquimod only: At the baseline visit, this group will receive instruction on imiquimod self application (16 week course) using a 6.25 mg vaginal suppository, storage of medication, possible side effects. Subjects will be provided a diary and case report form to record vaginal suppository application and side effects will be recorded per NCI Common Terminology Criteria for Adverse Events (CTCAE 4.0). Imiquimod self-application regimen will be similar to one previously described²⁴ and is as follows:
- Treatment weeks 1 and 2: Subjects apply one vaginal suppository per week
- Treatment weeks 3 and 4: Subjects apply two vaginal suppositories per week
- Treatment weeks 5 to 16: Subjects apply three vaginal suppositories per week

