Imiquimod will be dispensed in boxes containing 18 vaginal suppositories (treatment weeks 1-8) at the beginning of the treatment course. During follow up visit at week 8 (see below), subjects will be provided a new box of 24 vaginal suppositories to complete treatment course for weeks 9-16. Study drug will be prescribed by the investigator and may be dispensed either by the investigator or study staff.

6.2.2 Follow-up Visits: Follow-up visits will occur at week 8 (between weeks 7-9), at week 16 (between weeks 16-18) and once at week 22 (between weeks 20-24). For subjects randomized to treatment arms (2) Imiquimod only and (3) Imiquimod + HPV vaccine, the week 22 visit will occur at least 3 weeks after last dose of therapy. Urine pregnancy test will be performed at all follow-up visits. Subjects with exam findings concerning for worsening disease at any point in the study will be taken out of the study and treated with surgical excision procedure.

Week 8 (7-9 weeks) Visit: This visit will be timed to occur part way through the 16 week imiquimod treatment course. For women using imiquimod (Imiquimod only and Imiquimod + HPV vaccine arms), a review of medication diary, monitoring of correct use of study medication, and report of local and systemic side effects using a standardized case report form will occur at all follow up visits. For women who received HPV vaccine as part of study protocol (Imiquimod + HPV vaccine arm), a review of vaccination diary and report of local and systemic side effects using a standardized case report form will occur at all follow up visits. A pelvic exam with colposcopy will be performed to objectively assess for gross cervical lesions in all subjects and also for local side effects from imiquimod use in the Imiquimod only and Imiquimod + HPV vaccine arms. Endocervical cytobrush samples will be obtained at this time for study purposes. Cervical biopsies will be performed as clinically indicated. Blood sample collections will also occur. In addition, women in the Imiquimod + HPV vaccine groups who were previously unvaccinated will receive their booster dose of the HPV vaccine.

Week 16 (16-18 weeks) Visit: This visit will be timed to occur at completion of imiquimod treatment course. For women using imiquimod (Imiquimod only and Imiquimod + HPV vaccine

HIC#: 1603017415 Protocol version 11.0

CIN 2/3

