15.2 Analysis Set Definitions

- **full analysis set**—all randomized subjects
- safety analysis set—all subjects who have received at least one dose of any study drug, and/or have had any assessments at baseline or later that could be associated with an AE; analyzed by treatment received
- ITT analysis set—all randomized subjects with valid baseline measurements; analyzed by treatment assigned
- modified ITT analysis set—all randomized subjects with valid baseline measurements, receiving at least one dose of any study drug, and have at least one valid post-baseline measurement of outcome; analyzed by treatment assigned

HIC#: 1603017415 Protocol version 11.0

- modified ITT completers analysis set—all randomized subjects who receive at least one dose of
 any study drug and have complete and valid post-baseline assessments of outcome; analyzed by
 treatment assigned
- **per protocol analysis set**—all randomized subjects who receive all doses of their assigned study drug, have complete and valid post-baseline assessments of outcome, and have no protocol deviations (e.g. dose modification, assessment outside of time window, non-compliance)

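### Enrolling 138 (46 per arm) preserves the 38 per arm behind the power table only up to 17.4% dropout, not the stated 20%; if dropouts leave the analysis, the loss of power is small

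*Combined protocol and SAP*

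**What the plan says.** Section 15.8 sets the target before dropout: "We therefore aim to recruit a total sample size of 114 subjects (38 in each arm"). The operating-characteristics table in the same section is computed for that number, "given control group rate=0.28, n=38 subjects per arm", and gives power of 0.8269 for a 35-point difference at one-sided alpha of at most 0.025. The section then allows for losses: "Assuming a subject dropout rate of 20%, a total sample size of 138 (n = 46 per arm) subjects is calculated". It gives no inflation formula.

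Three other provisions decide what a dropout does to the analysed number:

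- Section 15.1: "Imputation of missing values will not be applied".
- Section 15.2: the modified ITT set, used for the main analysis under Section 15.5, is limited to randomised subjects with valid baseline measurements, "receiving at least one dose of any study drug, and have at least one valid post-baseline measurement of outcome".
- Section 15.8, evaluability paragraph: subjects whose efficacy cannot be determined stay in the analysis as 'unknown'. "This category will be listed and be reflected in the calculation of the response rate".

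**The concern.** A dropout allowance exists so that the number behind the power calculation is still there at the end. Here the allowance falls short at the plan's own dropout rate. Forty-six is what results from adding 20% to 38. Losing 20% of those enrolled requires dividing by 0.8, which gives a larger number.

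At stake is whether the enrolment target supports the power that the plan reports. There is little slack. The table's 82.7% at the target effect is already below the 90% implied by the general beta of 0.10 in Section 15.1, and a few further losses per arm bring it to about 80%.

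**Working it through.** **Inputs.** From Section 15.8: 38 evaluable per arm, 20% dropout, 46 per arm randomised (138 in total), control regression rate 0.28, and a target difference of 0.35, so 0.63 on active treatment. From Section 15.5: Fisher's exact test of each active arm against control at one-sided alpha 0.025.

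**Reproducing the plan's enrolment figure.** 38 × 1.2 = 45.6, rounded up to 46; 46 × 3 = 138. This matches exactly. That the plan used this formula is an inference, since none is stated.

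**What 46 per arm delivers.**

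- At 20% dropout: 46 × 0.8 = 36.8 per arm; 138 × 0.8 = 110.4 in total.
- Losses that still leave 38: 46 − 38 = 8, and 8/46 = 17.4%.
- Nine losses (9/46 = 19.6%) leave 37; ten (10/46 = 21.7%) leave 36.

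**What 20% dropout requires.** 38/(1 − 0.20) = 47.5, rounded up to 48 per arm; 48 × 3 = 144. Rounding does not explain the gap, because the unrounded total is 114/0.8 = 142.5.

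**Effect on power.** Power is the sum of binomial probabilities over all outcome pairs for which the one-sided Fisher p-value is at most 0.025, with rates 0.63 and 0.28.

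| Evaluable, treated/control | Exact power |
|---|---|
| 38/38 | 0.8269 (plan's table: 0.8269) |
| 37/37 | 0.8084 |
| 37/36 | 0.8260 |
| 36/37 | 0.8317 |
| 36/36 | 0.7885 |

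The first row reproduces the plan's own value. The rows are not monotone in sample size because the test is discrete.

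**Averaged comparison.** Assume that each subject drops out independently with probability 0.20, so the number retained per arm is binomial. Mean power is then 0.8132 from 46 per arm and 0.8316 from 48. The difference is 0.8316 − 0.8132 = 0.0184, or 1.8 points.

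**Conditions on the count.** The figure of about 110 holds if every dropout lacks a valid post-baseline outcome. Some may not. At the week 8 visit in Section 6.2.2, "Cervical biopsies will be performed as clinically indicated", and the week 16 visit has a similar provision, so some early leavers could have post-baseline histology. The plan does not say whether that would count as the outcome. The count also treats the control arm as analysable. Section 6.2.1 describes that arm as "Control group: Observation at specified study timepoints", while the modified ITT definition requires a dose of study drug. That is a separate defect.

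**The case against.** The arithmetic is hard to dispute, so the best objections concern weight and scope.

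**Size.** Expected losses at 20% are 46 × 0.2 = 9.2 per arm against the 8 covered, a gap of about one subject. The discreteness of Fisher's test moves power by as much: going from 38/38 to 38/37 (treated/control) raises it from 0.8269 to 0.8439. A planning dropout rate is not precise enough for 17.4% against 20% to change a decision. This stands, and it is why the point is minor and no extra enrolment is sought.

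**The range.** The 79% end belongs to 36 in both arms, which means 10 of 46 lost in each. A near-even split of 110 is 37/37/36, and its pairs give 80.8% to 83.2%. That is a fair refinement. The wider range covers whole-number arms of 36 or 37, either side of 36.8.

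**The 'unknown' rule.** If undetermined subjects stay in the denominator as non-responders, all 46 per arm are analysed and keeping 38 is no longer the relevant test. Assuming 20% unknown in each arm, the rates become 0.8 × 0.63 = 0.504 and 0.8 × 0.28 = 0.224, and exact power at 46 per arm is about 74.5%. That larger loss comes from the counting rule, not from the inflation error. It does not rescue the sentence, but it shows that the small effect reported here belongs to the modified ITT reading.

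**Meaning of dropout.** Subjects removed for worsening disease may have had a biopsy and so have a known outcome. This also stands, and it makes the evaluable count conditional.

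**Conclusion.** The concern holds as a minor arithmetic error. At the plan's own 20% dropout, 138 randomised leaves about 110 evaluable, not 114, and 38 per arm survives only up to 17.4% dropout. A correct inflation gives 144, six more than planned.

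Power at 63% against 28% stays at about 79–83% per comparison, against 82.7% in the plan's table. The average shortfall against 48 per arm is 1.8 points. These power figures assume that dropouts have no valid post-baseline outcome and leave the modified ITT set, and that observation controls are included in it. The averages further assume independent 20% dropout in each arm.

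**What to change.** Restate the dropout sentence in Section 15.8 in one of two ways, keeping 138:

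1. 138 randomised (46 per arm) keeps 38 evaluable per arm for dropout up to about 17%; or
2. 20% dropout leaves about 110 evaluable (about 37 per arm), with about 79–83% power per comparison at a 35-point difference.

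Either version should say that it assumes subjects without a valid post-baseline outcome are excluded under modified ITT, and this should be reconciled with the 'unknown' rule in the evaluability paragraph of Section 15.8.

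The same paragraph claims at least 90% power for effects of 29 points or more, while its own table gives 0.6860 at 30 points. That is a separate error, best corrected in the same edit.

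The dropout correction costs one sentence, with no extra enrolment and no change to the analysis.

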15.5 Analysis for the Primary Objective

The co-primary objectives of this study are to test superior treatment efficacy of Imiquimod + HPV vaccine (Trt1) compared to control (Trt0), and likewise Imiquimod only (Trt2) compared to control (Trt0). The primary outcome is *histologic regression* (yes/no) after completion of the 12 to 16 weeks imiquimod course. The full definition of *histologic regression* and how it is determined is described in Section 5.1.

The co-primary hypothesis tests are:

 $\{H_{01}: p_1 - p_0 = 0 \text{ versus } H_{11}: p_1 - p_0 > 0\}$ and

 $\{H_{02}: p_2 - p_0 = 0 \text{ versus } H_{12}: p_2 - p_0 > 0\}$

 p_0 , p_1 , and p_2 are the proportion of subjects on Trt0, Trt1, and Trt2, respectively, who are determined to have *histologically regressed*. Fisher's Exact Test will be used to assess if the data support rejecting the null hypothesis H_{01} , and likewise for H_{02} . To control Type I error, we will use a conservative Bonferroni adjustment for multiple comparisons with one-sided $\alpha = (0.05)/2 = 0.025$ as the significance level for each test. Rejection of a particular null hypothesis suggests superior efficacy of that specific treatment compared to control. Exact 95% confidence intervals will be calculated for p_1 - p_0 and for p_2 - p_0 . Confidence intervals for 'risk ratios' (p_1/p_0 , p_2/p_0) in addition to 'risk differences' (p_1 - p_0 , p_2 - p_0) may also be estimated. The main analysis will use the **modified ITT analysis set**. Sensitivity analyses for the same statistical method using the **modified ITT completers** and/or **per protocol analysis sets** may also be provided.

HIC#: 1603017415 Protocol version 11.0

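### Five upper-block alphas in the section 15.8 operating-characteristics table are wrong, and its unlabelled alpha makes the two blocks seem to conflict near the design effect

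*Combined protocol and SAP*

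**What the plan says.** The table in section 15.8 (Sample Size Justification) is described as "given control group rate=0.28, n=38 subjects per arm, one-sided α". It has two blocks, each covering differences of 0, 0.10, 0.20, 0.30, 0.32, 0.35, 0.37 and 0.40.

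- **Upper block**, headed "Exact binomial probabilities for α given minimum required power". The alphas are "0.5321 0.7745 0.1537 0.0366 0.0220 0.0118 0.0058 0.0027" for power of at least 0.80, and "0.4835 0.6574 0.2876 0.0863 0.0616 0.0363 0.0203 0.0103" for power of at least 0.90.
- **Lower block**: power when alpha is capped at 0.025 or 0.05. The powers under the 0.025 cap are "0.0147 0.1050 0.3472 0.6860 0.7472 0.8269 0.8706 0.9215".

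The text above the table names the test ("Calculations based on Fisher's Exact Test indicate we will have") and claims at least 90% power for a difference of 29 points or more at 0.025 per comparison. It describes the target effect thus: "we would like to have sufficient power to detect a 35% absolute increase in rate of histologic regression". Section 15.5 sets one-sided 0.025 "as the significance level for each test".

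**The concern.** Part of the upper block fails on inspection. At difference 0 the two arms share one rate, so power and alpha are the same probability, yet 0.8080 is paired with 0.5321 and 0.9033 with 0.4835. The lower block obeys the rule (0.0147 with 0.0147, 0.0305 with 0.0305). At 0 and 0.10, the 90% row carries a smaller alpha than the 80% row (0.4835 against 0.5321; 0.6574 against 0.7745). Enlarging a rejection region raises both power and alpha, so that order cannot occur. The alpha for 80% power also rises from 0.5321 to 0.7745 as the difference grows from 0 to 0.10, when it should fall.

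This is the only tabulated support for the sample size. If alpha is undefined and some cells are impossible, a reader may either distrust the sound cells or read power at the planned level from the wrong block.

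**Working it through.** **Inputs.** From section 15.8: 38 per arm, control rate 0.28, one-sided Fisher's exact test. From section 15.5: level 0.025 per comparison.

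**Formulas.** Let a and c be the numbers regressing on treatment and control, and b(x; 38, p) the binomial probability.

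- Fisher p-value: p(a,c) = P(X ≥ a), with X hypergeometric (76 subjects, a + c regressions, 38 on treatment).
- Power at nominal level L: Σ b(a; 38, 0.28+Δ) · b(c; 38, 0.28), summed over all (a,c) with p(a,c) ≤ L.
- Size at a common rate π: the same sum with both rates equal to π.
- Upper block: take the smallest L whose power reaches 0.80 or 0.90, then report the size of that region.

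**Step 1: reproduce the plan's figures.** With L = 0.025 and 0.05, all 16 lower-block powers reproduce to four decimals, including 0.8269 at 0.35. All 16 upper-block powers reproduce to within 0.0001, so the columns are aligned and the mismatch is not a text-extraction fault.

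**Step 2: find the alpha convention.** For one fixed rejection region (L = 0.025), the size at 0.28 is 0.0147 whatever the difference. The table's alpha row under that cap varies (0.0147, 0.0143, 0.0140, 0.0149), so size was not evaluated at 0.28. Taking π = 0.28 + Δ reproduces that row except at 0.10 (stated 0.0147, computed 0.0142), and all of the 0.05 row.

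**Step 3: apply that convention to the upper block.** Eleven alphas match to four decimals: 0.20 to 0.40 in the 80% row and 0.30 to 0.40 in the 90% row. Five do not:

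| Difference | Row | Nominal L | Power | Stated alpha | Size at 0.28+Δ | Size at 0.28 |
|---|---|---|---|---|---|---|
| 0 | 80% | 0.8646 | 0.8080 | 0.5321 | 0.8080 | 0.8080 |
| 0 | 90% | 0.9386 | 0.9033 | 0.4835 | 0.9033 | 0.9033 |
| 0.10 | 80% | 0.5926 | 0.8008 | 0.7745 | 0.4975 | 0.4515 |
| 0.10 | 90% | 0.7015 | 0.9010 | 0.6574 | 0.6381 | 0.6279 |
| 0.20 | 90% | 0.4046 | 0.9049 | 0.2876 | 0.2845 | 0.3445 |

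At 0.10 no common rate rescues the stated values: the largest size over all rates is 0.542 in the 80% row and 0.639 in the 90% row. A two-sided Fisher test does not rescue the five cells either.

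**Step 4: compare the blocks near the design.** The upper block shows only exact size. In the lower block the cap applies to the nominal Fisher level.

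| Difference | Upper block: power at alpha | Nominal L behind it | Lower block |
|---|---|---|---|
| 0.32 | 0.8011 at 0.0220 | 0.0325 | 0.7472 at α ≤ 0.025 |
| 0.35 | 0.9062 at 0.0363 | 0.0529 | 0.8898 at α ≤ 0.05 |
| 0.37 | 0.9012 at 0.0203 | 0.0325 | 0.8706 at α ≤ 0.025 |

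Each pair is correct on its own definition. The apparent gain at 0.37 is 0.9012 − 0.8706 = 0.0306, and at 0.32 it is 0.8011 − 0.7472 = 0.0539. Neither is available to a test that rejects at p ≤ 0.025.

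**Step 5: check the text.** At L = 0.025, power is 0.653 at 29 points, against the claimed 0.90 or more: a shortfall of about 0.90 − 0.653 = 0.247. Even at L = 0.05 it is 0.762. The table agrees with this calculation (0.6860 at 30 points).

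**The case against.** The strongest reply is that this is clerical. The impossible cells describe tests with alphas of roughly 0.5 to 0.8 at differences of 0 and 0.10, which nobody would use. The remaining upper-block error is 0.003. The 0.30 to 0.40 columns, which bracket the 35-point target, are right in both blocks. The table even shows that 90% power at 35 points costs more than 0.025, since 0.9062 is paired with 0.0363.

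Most of that stands. A reader might infer from the impossible cells that the whole upper block is unreliable. The documents do not support this: 11 alphas are exact at the treatment rate, including 0.1537, 0.0118 and 0.0363. They look wrong only if size is evaluated at 0.28 or at the average of the two rates. Overwriting them with values on another convention would introduce an inconsistency with the lower block.

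The reply does not dispose of the missing definition. Section 15.5 fixes a significance level, and a reader who compares 0.0203 with 0.025 at a difference of 0.37 will credit the design with 90% power that it lacks at that level. Nor does it answer the claim at 29 points, which the table itself contradicts.

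**Conclusion.** The point holds as a correction to a table and to the power statement beside it. Five of 16 upper-block alphas are wrong, by between 0.003 (0.2876 − 0.2845 = 0.0031) and 0.420 (0.9033 − 0.4835 = 0.4198). One lower-block alpha is off by 0.0005. Alpha is not defined, so the blocks seem to differ by 3 to 5 percentage points of power at 0.37 and 0.32, where both are in fact correct.

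A reader might go further and infer that 38 per arm rests on the bad cells. It does not: none of them lies at the planned level or near the target effect, and every tabulated power is right. What the sound row does show is that the design has 82.7% power at 35 points and about 65% at 29, so the text's figure of at least 90% at 29 points cannot stand.

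The result assumes 38 evaluable subjects per arm, a control rate of 0.28 and rejection at a one-sided Fisher p-value of at most 0.025. Treatment-rate evaluation of alpha is inferred from the match to the table, because the plan does not state it. The difference-0 error does not depend on that inference, and neither does the conclusion that both stated alphas at 0.10 are impossible.

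**What to change.** - In the upper block, replace 0.5321 with 0.8080, 0.4835 with 0.9033, 0.7745 with 0.4975, 0.6574 with 0.6381 and 0.2876 with 0.2845. Alternatively, drop the 0 and 0.10 columns and correct only the 0.20 cell. Leave the other 11 alphas unchanged.
- In the lower block under the 0.025 cap, change 0.0147 at 0.10 to 0.0142 if that column is kept.
- Add a note that every tabulated alpha is the exact size at the treatment rate, whereas the 0.025 and 0.05 caps are nominal Fisher levels. Preferably show the nominal cut-off beside each upper-block alpha (0.0325 for the 90% row at 0.37, for example).
- Name the α ≤ 0.025 power row as the design statement: 68.6% at 30 points, 82.7% at 35 and 92.2% at 40. Say that with 38 per arm, 90% power at 35 points needs a level above 0.025.
- Restate the claim of at least 90% power at 29 points to agree with that row. The next sentence's claims at 25 points need the same treatment, since exact power there at 0.025 is 0.516. Section 15.1 gives a default type II error of 0.10, so section 15.8 should say which power it adopts in its place.

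The cost is a corrected table and a few sentences. The test, the level and the 38 per arm are unchanged.
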